1.3. Schedule of Events

Table 1.1: Schedule of Events: Treatment Continuation Cohort

	Visits	SCR	BL	M3	M6	M9	M12	M15	M18	M21	EOT ^a	EOS/AE F/U ^b	Comment
	Window (Days)	0*	0*	±7	±7	±7	±14	±14	±14	±14	±7	±7	* SCR and BL will both occur on EOT visit of preceding study.
Assessments	Procedure												
Informed consent		X											Obtain prior to performing any study procedures
Eligibility assessment			X ^c										
Demographics/Medical history/Prior medications, non-drug therapies, and radiotherapy/Height	N/A												This information will be transferred from prior studies
Vitals	Vital signs and weight	X	X ^c	X	X	X	X	X	X	X	X		
PRO instruments	EQ-5D-5L		X ^c	X	X	X	X	X	X	X	X		Performed before any physical tests
	PROMIS PF		X ^c	X	X	X	X	X	X	X	X		Physical Function Scale performed before any physical tests
Safety	Physical exam	X	X ^c	X	X	X	X	X	X	X	X		Full PE on Screening and EOS, abbreviated PE at other visits. All PE exams will include functional assessment for the affected joint.
	ECG	X	X ^c								X		May be performed whenever deemed medically necessary and at any visit during which a subject exhibits a heart rate ≤50 bpm. Any abnormal finding should be confirmed with a repeated ECG. ECGs should be performed after vital signs assessments.

	Visits	SCR	BL	M3	M6	M9	M12	M15	M18	M21	EOT ^a	EOS/AE F/U ^b	Comment
	Window (Days)	0*	0*	±7	±7	±7	±14	±14	±14	±14	±7	±7	* SCR and BL will both occur on EOT visit of preceding study.
Assessments	Procedure												
AE	TEAE/SAE		X ^c					X			X		See Section 8.4.1
Concomitant medications, non-drug therapies, and radiotherapy	Concomitant		X ^c					X					
Laboratory assessments	Hematology		X ^c	X	X	X	X	X	X	X			See Section 10.2 for details
	Chemistry		X ^c	X	X	X	X	X	X	X			See Section 10.2 for details
	Urinalysis		X ^c		X		X		X		X		See Section 10.2 for details
	Coagulation		X ^c	X	X	X	X	X	X	X	X		See Section 10.2 for details
	Serum pregnancy test	X	X ^d								X		For females of reproductive potential (as defined in Section 5.1)
	Liver function tests		X	X	X	X	X	X	X	X	X		AST, ALT, ALP, total bilirubin, GGT, direct bilirubin
	Hormone testing		X ^c										Females only, FSH to confirm postmenopausal status
	TSH	X	X										
Treatment response/Disease assessment	MRI of affected joint		X ^c		X		X		X		X ^e		Tumor assessment. Additional imaging assessments may be performed with changes in tumor response(s), as deemed necessary by the Investigator.

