Dosing Diary	Provide Diary		X	X	X	X	X	X	X	X			Diary for pill count and AEs between scheduled clinic visits
	Review Diary			X	X	X	X	X	X	X	X		

	Visits	SCR	BL	M3	M6	M9	M12	M15	M18	M21	EOT ^a	EOS/AE F/U ^b	Comment
	Window (Days)	0*	0*	±7	±7	±7	±14	±14	±14	±14	±7	±7	* SCR and BL will both occur on EOT visit of preceding study.
Assessments	Procedure												
Study Drug: Pexidartinib	Dispense 3-month supply		X	X	X	X	X	X	X	X			
	Collect returned/Assess treatment compliance		X	X	X	X	X	X	X	X	X		
EOS Form												X	

AE = adverse event; BL = baseline; D = day; ECG = electrocardiogram; EOS = End of Study; EOT = End of Treatment; EQ-5D-5L = European Quality of Life Five Dimension Five Level Scale; FSH = follicle stimulating hormone; FU = Follow-up; M = month; MRI = magnetic resonance imaging; PRO = Patient-Reported Outcome; PROMIS PF = Patient-Reported Outcomes Measurement Information System – Physical Function; SAE = serious adverse events; SCR = screening; TEAE = treatment emergent adverse events; TVS = tumor volume score.

Note: For all visits, a month is considered a 30-day interval.

^a The EOT visit should occur within 7 days after the last dose of pexidartinib or at the time the decision is made to discontinue pexidartinib (if this is more than 7 days after the last dose of pexidartinib), unless there is a medical condition that prevents subjects from completing the visit within this time. The EOT visit must occur within 24 months after enrollment.

^b The End-of-Study will be reached with a follow-up phone call 1-month post-EOT visit to collect AE information.

^c Assessment does not need to be repeated if the procedure was done at End-of-Treatment visit of preceding study.

^d Urine pregnancy test at Screening only.

^e Only subjects who end their study participation early with no radiologic disease progression will have an additional MRI at 3 months ± 14 days after their last dose of study treatment or before any new TGCT therapy, including surgery, whichever occurs first. EOS will occur after this additional MRI.

Table 1.2: Schedule of Events: Treatment-Free Period of Treatment-Free/Re-Treatment Cohort

	Visits	SCR	BL	M1	M3/ M15	M6/ M18	M9/ M21	M12 ^a	M24	EOS/ AE F/U ^b	Comment
	Window (Days)	0*	0*	+ 28	±14	±14	±14	±14	±14	±7	** SCR and BL will both occur on EOT visit of preceding study.
Assessments	Procedure										
Informed consent		X									Obtain prior to performing any study procedures
Eligibility assessment			X								

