Note: In case of early discontinuation from the study, subjects must complete all the assessments corresponding to the M24 visit.

^a Subjects are allowed to continue past 12 months within the Treatment-Free period and will follow quarterly visits as per the 12-month visit until they enter the Re-Treatment period or the EOS, whereupon they will complete the EOS Visit and 30-day safety follow-up.

^b The End-of-Study will be reached with a follow-up phone call 1-month post-last study visit to collect AE information.

^c Assessment does not need to be repeated if the procedure was done at End-of-Treatment visit of preceding study.

Table 1.3: Schedule of Events: Re-Treatment Period^a of Treatment-Free/Re-Treatment Cohort

	Visits	BL-2	M1, M2 (LFT) ^a	M3	M6	M9	Mx ^b	EOT ^c	EOS/ AE FU ^d	Comment
	Window (Days)	0	±3	±3	±14	±14	±14	±7		
Assessments	Procedure									
Vitals	Vital signs and weight	X	X	X	X	X	X			
PRO instruments	EQ-5D-5L	X		X	X	X	X			Performed before any physical tests
	PROMIS PF	X		X	X	X	X			Physical Function Scale performed before any physical tests
Safety	Physical exam	X	X	X	X	X	X			Full PE on EOS, abbreviated PE at first re-treatment and at other visits. All PEs will include functional assessment for the affected joint
	ECG	X						X		May be performed whenever deemed medically necessary and at any visit during which a subject exhibits a heart rate ≤50 bpm. Any abnormal finding should be confirmed with a repeated ECG. ECGs should be performed after vital signs assessments.
AE	TEAE/SAE							X		
Concomitant medications, non-drug therapies, and radiotherapy	Concomitant					X				
Laboratory assessments	Hematology	X	X	X	X	X	X			See Section 10.2 for details
	Chemistry	X	X	X	X	X	X			See Section 10.2 for details
	Urinalysis	X	X		X		X	X		See Section 10.2 for details. Only perform every 6 months (ie, M12, M18, and M24)
	Coagulation	X	X	X	X	X	X			See Section 10.2 for details
	Serum pregnancy test	X	X	X	X	X	X	X		For females of reproductive potential (as defined in Section 5.1)
	Liver function tests ^a	X	X ^a	X	X	X	X	X		

	Visits	BL-2	M1, M2 (LFT) ^a	M3	M6	M9	Mx ^b	EOT ^c	EOS/AE FU ^d	Comment
	Window (Days)	0	±3	±3	±14	±14	±14	±7		
Assessments	Procedure									
	Hormone testing	X								Females only, FSH to confirm postmenopausal status
	TSH	X								

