8.4.5. Other Safety

Physical Examinations

A complete physical examination should include a weight measurement and an evaluation of the head, eyes, ears, nose, and throat and the cardiovascular, dermatological, musculoskeletal, respiratory, gastrointestinal, genitourinary, and neurological systems. Any abnormality identified at Baseline should be recorded on the General Medical History and Baseline Conditions eCRF. At subsequent visits (or as clinically indicated), limited, symptom-directed physical examinations should be performed. Changes from Baseline abnormalities should be collected in the subject's study record. New or worsened clinically relevant abnormalities should be recorded as AEs on the Adverse Event eCRF.

Vital Signs

Vital signs will include the measurements of respiratory rate, heart rate, systolic and diastolic blood pressures, temperature, height (may be obtained from subject's prior study file), and body weight [for Screening/Baseline this may be obtained from the subject's prior study]. Vital signs should be taken prior to ECG measurement. Blood pressure and pulse rate will be measured after the subject has rested in a recumbent position for at least 5 minutes and prior to laboratory draws.

Electrocardiograms

12 lead-electrocardiograms (ECGs) will be performed and recorded for every subject at Screening. The ECG will be measured after the subject has rested in a recumbent position for at least 5 minutes and the ECG results will be read locally. At any visit during which a subject exhibits a heart rate ≤ 50 bpm or other clinical indications for ECG, the ECG will be repeated. Any abnormal finding should be confirmed with a repeated ECG. Abnormal, clinically relevant findings occurring post-baseline will be reported as AEs. Whether or not the measurement is performed, the date the ECG is to be performed, heart rate, PR interval, RR interval, QRS amplitude, QT interval, QTcF interval, and results will be recorded in the eCRF.

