9.5.2. Safety Analyses

Safety analyses will be performed using the Safety Analysis Set and subjects will be analyzed by cohort separately.

Adverse Events

TEAEs are defined as new AEs or pre-existing conditions that worsen in CTCAE grade after the first dose of study drug and up to 30 days after last dose of study drug. AEs collected after 30 days after the last dose of study drug will not be considered TEAEs unless they are treatment related. AEs will be coded using the Medical Dictionary for Regulatory Activities (MedDRA) dictionary. An AE will be assigned to the study period in which it started, even if it resolved in a subsequent period. Incidence of TEAEs occurring over time, (e.g., 0 to 6 months, 6 to 12 months, etc.) will be summarized. The number and percentage of subjects reporting TEAEs will be calculated overall, by system organ class, by preferred term, and by cohort.

TEAEs will be further summarized by CTCAE grade and relationship to study drug. Similarly, the number and percentage of subjects reporting treatment-emergent SAEs and related treatment-emergent SAEs will be tabulated, and TEAEs leading to discontinuation of study drug.

A by-subject AE (including treatment-emergent) data listing including but not limited to verbatim term, preferred term, system organ class, CTCAE grade, and relationship to study drug will be provided. Deaths, other SAEs, AESIs, and AEs associated with study drug discontinuation, will be listed. AEs due to COVID-19 will be also summarized and listed.

Clinical Laboratory Evaluation

Descriptive statistics will be provided for the clinical laboratory results by scheduled time of evaluation and by cohort, as well as for the change from Baseline. The Baseline value is defined as the last non-missing value before the initial administration of study drug. In addition, mean change from Baseline will be presented for the maximum and minimum post-treatment values and the values at the EOT visit.

Abnormal clinical laboratory results will be graded according to NCI-CTCAE version 5.0, if applicable, and the grade will be presented in a by-subject data listing. A shift table, presenting by cohort the two-way frequency tabulation for baseline and the worst post-treatment value according to the CTCAE grade, will be provided for clinical laboratory tests. A listing of abnormal clinical laboratory test results deemed of clinical significance or of Grade 3 or 4 will be generated.

ECG

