Descriptive statistics will be provided for the ECG measurements by scheduled time of evaluation and by cohort, as well as for the change from Baseline. The Baseline value is defined as the last non-missing value before the initial administration of study treatment. A listing of ECG data will be generated.

Vital Signs

Descriptive statistics will be provided for the vital sign measurements by scheduled time of evaluation and by cohort, as well as for the change from Baseline. The Baseline value is defined as the last non-missing value before the initial administration of study treatment. A listing of vital sign data will be generated.

Other

Listings of all other safety endpoints (e.g., physical examination findings) will be generated.

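### ECG intervals are summarised only by scheduled time, with one late ECG after each period's baseline, so the plan gives no incidence of abnormal interval values and no assured on-drug ECG.

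*Combined protocol and SAP*

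**What the plan says.** Tables 3.1 and 3.2 list ECGs, with adverse events and laboratory assessments, in the incidence-type safety endpoint of both cohorts. Section 9.5.2 gives ECG two outputs. One is a summary: "Descriptive statistics will be provided for the ECG measurements by scheduled time of evaluation and by cohort", with change from Baseline. The other is: "A listing of ECG data will be generated". Section 9.5.3 plans nothing further. For laboratory results the same section goes beyond scheduled times: "mean change from Baseline will be presented for the maximum and minimum post-treatment values", and a shift table uses the worst CTCAE grade.

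Outside the scheduled times, the ECG rows of Tables 1.1 to 1.3 (section 1.3) state: "May be performed whenever deemed medically necessary and at any visit during which a subject exhibits a heart rate ≤50 bpm". Section 8.4.5 words the response to a low heart rate differently: "or other clinical indications for ECG, the ECG will be repeated".

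On timing, the footnotes to Tables 1.1 and 1.3 say: "The EOT visit should occur within 7 days after the last dose of pexidartinib". They allow a later EOT visit when the decision to stop comes more than 7 days after that dose. For the Treatment-Free period, a note to Table 1.2 adds: "In case of early discontinuation from the study, subjects must complete all the assessments corresponding to the M24 visit".

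**The concern.** A summary by scheduled time can show only what was scheduled, and here that is a baseline ECG and one ECG at the end of the period. The ECGs most likely to be abnormal are those taken in between for a reason, and the plan does not say where they are tabulated. A mean change at one late visit does not tell a reader how many subjects had a prolonged PR or QTcF at any time on pexidartinib. An incidence endpoint calls for that number.

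The late ECG has a second weakness in the two treated groups. It may come after the last dose. In the Continuation Cohort, Baseline is the EOT visit of the prior study, at which the subject is still dosing (section 4.1.1). The reported change could then compare an on-drug value with one taken after dosing stopped, with nothing in the table to show it.

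**Working it through.** The plan states no figure to reproduce, and no power or sample-size calculation bears on the point. The check is a count from the schedule, set beside the analysis text.

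1. **Scheduled ECGs, from the ECG rows of section 1.3.**
   - Table 1.1 (Continuation): Screening/Baseline on the same day, then EOT. Visits between without a scheduled ECG: M3, M6, M9, M12, M15, M18, M21 = 7.
   - Table 1.2 (Treatment-Free): Baseline, then M24 (also done at early discontinuation). Visits between: M1, M3, M6, M9, M12, M15, M18, M21 = 8.
   - Table 1.3 (Re-Treatment): BL-2, then EOT. None at M1, M2, M3, M6, M9 or Mx.
   - Each period therefore has 1 scheduled ECG after its own baseline. A subject who is re-treated has 3 in all: Baseline, BL-2 and EOT.

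2. **Longest gap between scheduled ECGs.** At most 24 months; at the stated 30 days per month, 24 × 30 = 720 days.

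3. **Where a triggered ECG goes.**
   - Summary by scheduled time: no place stated.
   - Listing: yes.
   - AE tables: only through judgment. Section 8.4.5 sends clinically relevant abnormal findings to AE reporting. Section 8.4.1 covers isolated ECG findings that are symptomatic, lead to dose reduction or stopping, need treatment, or are AEs in the investigator's view. An asymptomatic PR or QTcF change judged not relevant appears in the listing alone.

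4. **What the vital-signs summary covers.** Heart rate is a vital sign (section 8.4.5). In Table 1.1 vital signs are taken at all 7 intermediate visits and at EOT, and section 9.5.2 summarises them by scheduled time. Heart rate on treatment is therefore tabulated. PR, QRS, QT and QTcF are not.

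5. **Laboratory and ECG side by side (section 9.5.2).** Laboratory: scheduled times, maximum, minimum, worst-grade shift, listing. ECG: scheduled times, listing.

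6. **On-drug status of the late ECG.** EOT may fall 0 to 7 days after the last dose, or later. The number of scheduled post-baseline ECGs assured to be on drug is therefore 0 in the Continuation Cohort and 0 in the Re-Treatment period. In the Treatment-Free period M24 is off drug by design, so the point does not arise there.

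7. **How much drug could remain at day 7.** The documents give no half-life, so this is an assumption shown over a range. Fraction remaining = 0.5^(168 h / half-life):
   - 12 h: 0.5^14 = about 0.006%
   - 24 h: 0.5^7 = about 0.8%
   - 72 h: 0.5^2.33 = about 20%

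   Whether such an ECG is effectively off drug cannot be settled from the documents.

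**The case against.** The strongest reply is that the matter is mostly covered. Low heart rate appears in the vital-signs summary at the visits in question. Clinically relevant ECG findings enter the TEAE tables by number and percentage. The listing holds every value. The study is descriptive, and its only special-interest text concerns the liver; no section describes a QT or PR risk. The laboratory shift table rests on CTCAE grades, so equal treatment of ECG is not automatic. Section 9.5 calls itself a summary and leaves detail to a SAP to be finalised before database lock. All of this stands, and it narrows the gap to ECG intervals not reported as AEs. It does not supply the missing count.

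The documents do not support several stronger readings that a reader might infer:
- *That triggered ECGs can never enter the summary, or that none from the 7 visits will.* This is an inference from the scheduled-time wording. Nothing excludes them, and an ECG triggered at M6 is taken at a scheduled visit and might be tabulated there.
- *That bradycardia on drug would go unseen.* The vital-signs summary and listing cover it.
- *That each subject has one ECG after study baseline.* Re-treated subjects also have BL-2.
- *That the EOT ECG is off drug.* It may be, but this is not shown. Section 6.1 has dosing run daily to the subject's end of study, and section 6.2.2 tells subjects to take their usual doses on visit days, so a late EOT mainly concerns early discontinuers.
- *That EOT may come about 28 days after the last dose.* This takes the 4-week hold in Table 6.3 alone. The text of section 6.5 requires discontinuation once a toxicity interruption exceeds 14 days, unless the Medical Monitor agrees to continue. Those passages must be reconciled before any such figure can be used.

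**Conclusion.** The point holds as a limited, low-cost improvement. Section 9.5.2 gives no incidence of abnormal ECG interval values. It states no place for ECGs triggered between a period's baseline and its single later scheduled ECG. It has no assured on-drug post-baseline ECG in the two treated groups.

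In size, 7 visits in the Continuation Cohort, 8 in the Treatment-Free period and every visit between BL-2 and EOT in the Re-Treatment period lack a scheduled ECG, with up to 24 months between scheduled recordings. How many abnormal values this would leave untabulated cannot be estimated, since the documents give no rate of triggered or abnormal ECGs.

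The conclusion assumes that the summary is programmed as worded, and that no later SAP text adds a worst-value rule; the document supplied contains none. The difference between "or other clinical indications for ECG, the ECG will be repeated" and "May be performed whenever deemed medically necessary and at any visit during which a subject exhibits a heart rate ≤50 bpm" is a separate inconsistency. It matters here because the number of triggered ECGs depends on how each site reads it.

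**What to change.** In section 9.5.2, or in the SAP before database lock, add one table by cohort and period:
- each subject's worst post-baseline ECG values (for example longest QTcF and longest PR) from all ECGs, scheduled and unscheduled, reported as numbers of subjects in pre-specified categories; the documents give no cut-points, so the sponsor must state them in advance;
- the number of subjects with at least one triggered ECG, so that the reader can see how far the counts depend on ECGs being ordered;
- days since last dose for EOT ECGs, with those taken after the last dose shown separately.

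Reconcile the trigger wording in section 8.4.5 with that in Tables 1.1 to 1.3.

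The cost is one more table. Section 8.4.5 already has heart rate, PR, QT and QTcF recorded in the eCRF, so no visit or procedure is added. The drawback is that triggered ECGs are a selected sample: they support counts of subjects, not means, and the scheduled-time summary should remain beside the new table.

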9.5.3. Other Analyses

No other analyses are planned in this study.

9.6. Interim Analyses

Not applicable.

10. APPENDICES – SUPPORTING DOCUMENTATION AND OPERATIONAL CONSIDERATIONS

10.1. Appendix 1: Regulatory and Ethical Considerations

10.1.1. Regulatory Compliance

The study protocol, the Investigator Brochure, available safety information, recruitment procedures (e.g., advertisements), subject information and consent form, any subject written instructions to be given to the subject, information about payments and compensation available to the subjects, and documentation evidencing the Investigator's qualifications should be submitted to the independent IRB or IEC for ethical review and approval according to local regulations, prior to the study start. The written approval should identify all documents reviewed by name and version.

Changes in the conduct of the study or planned analysis will be documented in a protocol amendment and/or the SAP. Written approval of all protocol amendments and changes to any of the above listed documents must be obtained from the IRB, IEC, and/or applicable regulatory authorities.

The Investigator should notify the IRB or IEC of deviations from the protocol or SAEs occurring at the study site and other AE reports received from the Sponsor/CRO, in accordance with local procedures.

The Sponsor will appoint a Coordinating Investigator. Among other possible duties, the Coordinating Investigator will be responsible for reviewing the Final Clinical Study Report and testifying to the accuracy of the description of the study conduct. Because the Coordinating Investigator should have personal knowledge of the conduct of the study, he or she will normally be chosen from among those Investigators who have enrolled and treated at least 1 subject. However, where an Investigator has special knowledge of the field or of the study, the Coordinating Investigator can be chosen prior to enrollment of the first subject. In all cases, the Coordinating Investigator must be chosen prior to locking the database.

Compliance Statement, Ethics, and Regulatory Compliance

This study will be conducted in compliance with the protocol, the ethical principles that have their origin in the Declaration of Helsinki, the International Council for Harmonization (ICH) consolidated Guideline E6 for Good Clinical Practice (GCP) (CPMP/ICH/135/95), and applicable regulatory requirement(s) including the following:

- European Commission Directive (2001/20/EC Apr 2001) and/or;
- European Commission Directive (2005/28/EC Apr 2005) and/or;
- US Food and Drug Administration (FDA) GCP Regulations: Code of Federal Regulations (CFR) Title 21, parts 11, 50, 54, 56 and 312 as appropriate and/or;
- Japanese Ministry of Health, Labor and Welfare Ordinance No. 28 (27 Mar 1997) and/or;

- The Act on Securing Quality, Efficacy and Safety of Pharmaceuticals, Medical Devices, Regenerative and Cellular Therapy Products, Gene Therapy Products, and Cosmetics No. 1 (25 Nov 2014);
- Other applicable local regulations.

In addition, the Investigator will inform the Sponsor in writing within 24 hours of any urgent safety measures taken by the Investigator to protect the study subjects against any immediate hazard(s), and of any suspected/actual serious GCP non-compliance brought to the attention of the Investigator.

Supply of New Information Affecting the Conduct of the Study

When new information becomes available that may adversely affect the safety of subjects or the conduct of the study, the Sponsor will inform all Investigators involved in the clinical study, ECs/IRBs, and regulatory authorities of such information, and when needed, will amend the protocol and/or subject information.

The Investigator should immediately inform the subject whenever new information becomes available that may be relevant to the subject's consent or may influence the subject's willingness to continue participation in the study. The communication should be documented on medical records, for example, and it should be confirmed whether the subject is willing to remain in the study.

If the subject information is revised, it must be re-approved by the EC/IRB. The Investigator should obtain written informed consent to continue participation with the revised written information even if subjects were already informed of the relevant information. The Investigator or other responsible personnel who provided explanations and the subject should sign and date the revised ICF.

